People who live with HIV (PLWH) experience a high incidence of neurocognitive deficits and HIV-associated non-AIDS (HANA) disorders, including cardiovascular disease (CVD), metabolic dysfunction, and autonomic decline. While antiretroviral treatment (ART) has reduced AIDS-related morbidity, both the virus and the medications are associated with lipid disorders that also increase CVD risk, including dyslipidemia and lipodystrophy. Consequently, the development of effective lifestyle interventions to reduce the incidence of HIV-associated neurocognitive disorders (HAND) and decrease metabolic disorders is a high priority. Physical activity (PA) has been utilized as an effective tool to improve health in PLWH, but may not be sufficient by itself to improve lipid levels. Existing PA interventions in PLWH typically required strenuous PA and significant resources that limit feasibility for many people living with the disease. Recent work indicates that interrupting periods of sedentary behavior (SB), independent of PA, also has a significant beneficial effect on metabolic function, but SB has not been well-studied in PWLH. Mediterranean-style diets (MedDiet) are also effective at improving CVD risk factors in HIV-uninfected individuals and are reported to reduce cognitive decline in persons at risk for Alzheimer's disease, but have not been widely tested in PWLH. We recently developed a novel and personalized Short Message Service (SMS) mobile phone text messaging intervention (iSTEP) that is designed to increase moderate PA in PLWH. Our objective is to expand upon this work and conduct an RCT examining the efficacy of iSTEP in combination with a mobile mHealth MedDiet intervention tailored to PLWH. 150 PLWH will be randomly assigned to a control group ($n = 50$), a 6-month iSTEP group with just a PA/SB intervention ($n = 50$), or a 6-month intervention with both PA/SB and MedDiet components ($n = 50$), where participants receive daily interactive SMS/MMS messages designed to increase moderate PA, reduce SB, and promote adherence to a MedDiet, including walnut consumption. PA/SB will be quantified by accelerometer, Fitbit step counts, and self-report, while MedDiet adherence will be assessed by self-report (Diet History Questionnaire and weekly SMS feedback) and also objective measures (polyunsaturated fatty acid levels - PUFA in blood). We will also conduct a follow-up assessment 6 months after the end of the intervention (accelerometer, neurocognitive testing, PUFA levels) to assess PA and MedDiet adherence. We hypothesize that iSTEP (both intervention arms) will increase PA, reduce SB, and improve neurocognition compared to control; the iSTEP + MedDiet group will demonstrate improvement in CVD risk factors and neurocognition compared to the PA intervention alone. Findings from this proposal will lay the groundwork for development of novel large-scale mobile PA/diet interventions dedicated to treating HAND and improving cardiovascular health for PLWH.

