4.0 CLINICAL MANAGEMENT ISSUES

4.1 Adverse Events

We have taken great care to minimize the risks associated with text messaging in this study, including eliminating any information in the SMS content that could identify the HIV status of the participants. For example, we will not use any medication names in messages (e.g., identifying an HIV medication) or include content that could be used by a third party to identify a particular medical condition, but will utilize generic messages that ask about relevant physical conditions and limitations (e.g., do you have muscle aches today?). We will not include any personally identifiable information such as the name of the participant in the SMS content sent to each subject or stored on mobile phones provided to participants. Text messages will include geographical landmarks such as nearby locations to engage in PA or the names of specific grocery stores to purchase food items; there is a risk this information could be accessed by an unauthorized person if the cell phone is lost or stolen.

Participants may experience anxiety or embarrassment related to one's personal PA or diet behavior (e.g., a lack of physical activity) or feelings of inadequacy with limited progress during the intervention. Participants in the focus groups may experience nervousness from participating in a group process activity or speaking in front of others regarding the issues that may affect PA or diet. Participants will be motivated to engage in moderate PA, including walking, and light PA to reduce and interrupt SB. No vigorous PA will be required. Some participants may experience mild muscle fatigue or soreness. Standard clinical interview procedures, including administration of PA and diet questionnaires, pose little risk to

participants. The blood draw procedure includes the risk of minor discomfort, bruising, fainting, or dizziness.

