5.0 STATISTICAL ANALYSIS PLAN

5.1. Analyses.

For all analyses, two-sided tests with significance level $\alpha=0.05$ will be used. Where necessary, assumptions for parametric testing will be checked prior to analyses. If assumption of normal distribution is not met, variable transformation (e.g., log) or nonparametric methods will be used. Randomization scheme should insure comparability of the groups on demographic and medical characteristics. Baseline characteristics will be compared between the groups using ANOVA for numeric values (e.g., age) and chi-square test for categorical variables (e.g., gender). Baseline characteristics found to be different between the groups will be used as covariates in the primary analyses to control for possible effect of group differences on the outcomes. For the primary analysis, PA outcomes will be measured at 2 visits (baseline (BL) and 24 weeks) with the exception of accelerometer and 7DPAR data, which will be measured at 3 visits (BL, 24 weeks, and 48 weeks); cognition and cardiovascular risk factors will also be assessed at 3 visits. Mixed models analyses will be conducted with a) the inclusion of all available data, assuming values missing at random; b) the baseline carry forward (BOCF) imputation method; and c) including only the participants who complete the study. For Hypothesis 1.1, changes in numeric outcomes measuring PA (e.g., time spent on PA, time spent on sedentary behavior) from baseline to week 24 (to week 48 for accelerometer/7DPAR measures) will be compared between the iSTEP and control groups using mixed effects models with subject-specific random effect. Subject-specific random effects will estimate individual changes in outcomes (slopes) as well as individual baseline values (intercept) to take into account natural variability in measured values between subjects. The models will regress PA measures on group (iSTEP vs. control), time (2 time points), and their interaction. A significant interaction term ($p<0.05$) would indicate a significant treatment effect or, in other words, significant differences in mean changes in outcomes over time (slopes) between the two treatment groups. Mixed effects model with terms for group, time (3 visits), and their interaction will be used to evaluate effect of iSTEP intervention on changes in accelerometer values. In explorative analysis, we will compare daily

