changes in PA variables measured daily (step count, time spent in PA, and time in SB) between iSTEP and control groups using similar method as above, except using many time points (days) instead of just 2 or 3. For Hypothesis 1.2, Global Mean T-score will measure cognitive performance at all visits; practice effect correction will be applied to values measured at the 24 and 48 weeks. Again, mixed effects model with subject-specific random effect will be used to regress T-score on group (iSTEP vs. control), time (3 time points), and their interaction. We hypothesize that a significant interaction term will show that the slope representing an improvement in cognition will be the smallest for the control group and the largest for the iSTEP group. Similarly, for Hypothesis 2.1, changes in multiple numeric outcomes related to cardiovascular disease risk factors (e.g., cholesterol) will be evaluated with separate mixed effects models. The models will regress the outcomes on group (control, iSTEP PA/SB, iSTEP PA/SB + MedDiet), time (3 time points), and their interaction, including subject specific random effect. We hypothesize that a significant interaction will be observed and that it will show greater improvements in the outcomes for iSTEP groups, with iSTEP PA + MedDiet group having the best results. Similar approach will be used for Hypothesis 2.2, were changes (slopes) in Global Mean T-scores will be compared between the iSTEP PA/SB + MedDiet and iSTEP PA/SB groups and between the iSTEP PA + MedDiet group and controls. Additional analyses: We will conduct exploratory analyses using mixed models to assess changes in diet markers (omega-3, DHA, EPA, percent fat intake on the DHQ) over time to assess if there are group differences and if these markers predict CVD/NP outcome. Multiple regression analyses will be conducted across all participants to examine which factors (PA amount, SB change, MedDiet Score) significantly predict NP and CVD risk factors, including metabolic measures and inflammatory markers at the 6-month and 12-month visits. We will collect Likert scale data that identify what aspect of iSTEP is most useful (e.g., step self-monitoring, step count goals, types of PA/SB messages, comparing PA data to other PLWH) and conduct regression analyses to identify factors (e.g., PA barriers, SMS adherence) that best predict study outcome and PA/diet maintenance.

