5.2 Power Analysis

For all power calculations 20% dropout rate is assumed based on prior mHealth diet interventions¹¹⁹, leaving N=40 for each of the three groups.

For mixed effects models comparing change in outcomes over time between groups, estimates of power depend on intra-class correlation (within-subject correlation of outcomes measured at different times) and number of total visits, including baseline. For models based on 2 visits (hypothesis 1.1, except accelerometer), there will be at least 80% power to detect a medium to large effect size, Cohen's d , for the difference in mean change in outcomes from baseline to week 24 visit (Fig 1a). For models based on 3 visits (accelerometer /7DPAR values in hypothesis 1.1; hypotheses 1.2 through 2.2), there will be at least 80% power to detect a large effect size, d , for mean differences in outcome changes over three visits between any of the two groups (Fig 1b).

[figure not shown]

Figure 1a. Comparing changes in PA outcomes between iSTEP group ($n = 40$ after 20% dropout) and controls ($n = 40$ after 20% dropout) from BL to week 24. **Figure 1b.** Comparing changes in accelerometer data, cardiovascular disease risk factors, or cognitive outcomes between iSTEP PA+MedDiet and either of the other two groups ($n = 40$ for each group after 20% dropout) from BL to 48 weeks.

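### Hypothesis 1.1 does not rank the self-reported 7DPAR below the accelerometer, so a 7DPAR-only result could be declared an effect on physical activity in participants who know they are coached

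*Combined protocol and SAP*

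**What the plan says.** The opening summary names three sources for activity and sedentary time: "PA/SB will be quantified by accelerometer, Fitbit step counts, and self-report". The abbreviation 7DPAR is never spelled out. Since it is listed separately from the accelerometer and is not the Fitbit, it is most naturally read as the self-report source.

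Section 5.1 introduces the primary analysis by giving activity outcomes two visits, "with the exception of accelerometer and 7DPAR data, which will be measured at 3 visits". For Hypothesis 1.1 it compares changes "from baseline to week 24 (to week 48 for accelerometer/7DPAR measures) will be compared between the iSTEP and control groups". Section 5.2 pairs the two again, as "accelerometer /7DPAR values in hypothesis 1.1".

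For every analysis, "two-sided tests with significance level $\alpha=0.05$ will be used". The criterion in Hypothesis 1.1 covers all activity measures: "A significant interaction term ($p<0.05$) would indicate a significant treatment effect".

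Section 5.1 names no single primary activity measure, sets no order among them and has no rule for discordant results. Its three analysis sets (all available data, baseline carried forward, completers) deal with missing data only.

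**The concern.** The person who supplies a self-report outcome here also knows the allocation. The summary describes daily interactive messages over six months that promote activity and discourage sitting. The additional analyses in 5.1 list among the iSTEP components "step count goals, types of PA/SB messages, comparing PA data to other PLWH". Section 4.1 anticipates that participants may have "feelings of inadequacy with limited progress during the intervention". The plan mentions no masking, and someone who receives coaching texts cannot be blind to them.

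Over-reporting that is the same in all arms cancels in the group-by-time term. Over-reporting brought on by coaching does not: it goes into the tested interaction in the direction of the hypothesis, and a larger sample would only make it more likely to reach significance. Under the rule as written, a change in reporting could be recorded as a change in activity, even though the trial also collects a device measure of that activity.

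**Working it through.** **The plan's own figure.** Section 5.2 assumes 20% dropout from 50 per arm: 50 × (1 − 0.20) = 40, as stated. With 40 v 40, two-sided alpha 0.05 and 80% power, the detectable difference in mean change is (1.960 + 0.842) × √(2/40) = 0.626 SD. This is consistent with the verbal claim of a medium to large effect. The power curves are not shown, so only that claim could be checked. No stated figure is wrong.

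**Inputs for the bias calculation.**
- From the documents: alpha 0.05 two-sided and 40 evaluable per arm.
- Both 40 v 40 (the Figure 1a caption) and 80 v 40 (both iSTEP arms pooled against control) are shown, because the summary words the activity hypothesis for both intervention arms.
- Assumed: no true effect, and an arm difference in over-reporting of b = 0.15 to 0.30 SD of change.

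**Formula.** For a two-sample t-test on change, the noncentrality is b / √(1/n₁ + 1/n₂) with n₁ + n₂ − 2 degrees of freedom. The rejection probability is the noncentral-t mass beyond the two-sided 5% critical values.

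| b (SD of change) | n | standard error | noncentrality | P(p<0.05), no true effect |
|---|---|---|---|---|
| 0.15 | 40 v 40 | 0.2236 | 0.671 | 10.2% |
| 0.30 | 40 v 40 | 0.2236 | 1.342 | 26.3% |
| 0.15 | 80 v 40 | 0.1936 | 0.775 | 12.0% |
| 0.30 | 80 v 40 | 0.1936 | 1.549 | 33.6% |

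A normal approximation gives 26.9% and 34.1% at b = 0.30. At b = 0 the rate is 5%. The same 5% applies to the accelerometer whatever b is, because reporting does not enter that measure.

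**Does this carry over to the three-visit model?** Section 5.1 describes the interaction as a difference in slopes, and coaching ends at week 24.
- *Linear time.* With visits at 0, 24 and 48 weeks and complete data, the least-squares slope weights are proportional to (0 − 24, 24 − 24, 48 − 24) = (−24, 0, 24). Week 24 has zero weight, so bias present at week 24 but gone by week 48 adds essentially nothing.
- *Categorical time.* The week-24 contrast has its own term, so bias at week 24 enters the test.
- *Bias that lasts to week 48.* It enters under either coding.

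Section 5.1 does not say how time is coded. The table is a single change-score calculation and applies to the 7DPAR model only in the second and third cases.

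**The case against.** The strongest reply is that the false effect needs bias that differs by arm, and that the documents do not establish it. What controls receive is not described. Section 4.2 does not limit by arm its counselling on raising step counts gradually or its texts about adverse events. The exploratory analysis compares daily step counts between iSTEP and control, so controls seem to be monitored too. Self-monitoring of steps might even make reports more accurate. This stands: a reader might infer that controls face no pressure to over-report, and the text does not support that. It leaves the size of the bias open. It does not remove the gap in the rule.

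A second reply is that the accelerometer is already the lead in practice. The sentence in 5.1 that specifies the three-visit model names only accelerometer values, the Figure 1b caption names the accelerometer and not the 7DPAR, and so does the summary's list of follow-up measures. These are hints of intent. None ranks the measures, while 5.1 pairs them twice and 5.2 once.

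A third reply is that a null accelerometer result would be visible beside a positive 7DPAR. That is so, but the plan does not say which of the two would then decide.

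**Conclusion.** The concern holds as a gap in the decision rule: Hypothesis 1.1 lets a self-report measure establish an effect on activity by itself. That conclusion rests on two inferences, both reasonable: that the 7DPAR is self-report, and that coached participants know they are coached.

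The 10% to 26% (40 v 40) and 12% to 34% (80 v 40) are sensitivity figures under an assumed bias, not estimates of this trial's error rate. A reader might infer that the 7DPAR test is known to run well above 5%. The documents do not support that, since they give no reporting difference, and under a linear slope bias that fades after coaching would add little.

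The point is worth acting on because the correction is small and limits what the trial could wrongly conclude.

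**What to change.** State in 5.1 that the accelerometer measure decides Hypothesis 1.1 and that the 7DPAR is supportive. Add that a significant 7DPAR result without accelerometer support will be reported as a change in reported activity, not as an effect on physical activity.

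The cost is a few words in the analysis plan, with no new visits or data. The price is that a significant 7DPAR result alone can no longer be claimed as an effect.

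A model of the within-person difference, 7DPAR minus accelerometer, may look like a natural addition. It should not be added unless the two measures are shown to share units and to cover the same week. The documents establish neither, and if the scales differ, a true increase in activity could appear as misreporting.

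### For PA outcomes measured only at baseline and week 24, the stated random intercept plus random slope is not identified, and no fallback covariance structure is named

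*Combined protocol and SAP*

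**What the plan says.** Section 5.1 sets the schedule: "PA outcomes will be measured at 2 visits (baseline (BL) and 24 weeks"). Two instruments are then set apart, "with the exception of accelerometer and 7DPAR data, which will be measured at 3 visits (BL, 24 weeks, and 48 weeks"). The same three visits apply to the cognitive and cardiovascular outcomes.

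For Hypothesis 1.1, changes are compared between groups "using mixed effects models with subject-specific random effect". The plan then spells out what that means: "Subject-specific random effects will estimate individual changes in outcomes (slopes) as well as individual baseline values (intercept"). The next sentence applies this to the two-visit case: "The models will regress PA measures on group (iSTEP vs. control), time (2 time points), and their interaction". The three-visit accelerometer model is described afterwards, in a separate sentence.

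The treatment effect is judged on a fixed effect: "A significant interaction term ($p<0.05$) would indicate a significant treatment effect". The general rule is that "two-sided tests with significance level $\alpha=0.05$ will be used".

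Three versions of the mixed model are planned: all available data under missing at random (MAR), baseline carried forward, and completers only. The plan states no random-effects covariance, no residual structure, no exception for two-visit outcomes and no fallback model.

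**The concern.** A participant seen twice yields one observed change. That change mixes a real individual trend with visit-to-visit error, and nothing else in the data for that outcome separates the two. A model with a random intercept, a random slope, their covariance and a residual asks for that separation.

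Two things are at stake. First, the plan promises individual-change estimates that this schedule cannot deliver. Second, if the program refuses the model or warns, the analyst must choose another covariance structure after seeing data, in an analysis the plan calls primary. In the all-available-data version, that choice can affect the treatment estimate.

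**Working it through.** **1. The plan's own figure.** Section 5.2 states that "20% dropout rate is assumed based on prior mHealth diet interventions". 50 × (1 − 0.20) = 40 per group, as stated. At 80% power and two-sided 0.05, the detectable difference is (1.960 + 0.842) × √(2/40) = 0.626 SDs of change. In baseline-SD units this is multiplied by √(2(1 − ρ)). For assumed within-participant correlations ρ of 0.3, 0.5 and 0.7 it gives 0.74, 0.63 and 0.49. That agrees with the plan's description of a medium to large effect. The text gives no numerical d or ρ. The point below does not change this calculation.

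**2. Counting parameters.** Code time as 0 and 1. Let g11 be the intercept variance, g22 the slope variance, g12 their covariance and s the residual variance. Then

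- V11 = g11 + s
- V12 = g11 + g12
- V22 = g11 + 2·g12 + g22 + s

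The rank of this map shows what can be identified:

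| Visits | Random effects | Parameters | Moments | Rank | Identified? |
|---|---|---|---|---|---|
| 2 | correlated | 4 | 3 | 3 | no |
| 2 | uncorrelated | 3 | 3 | 3 | only just |
| 3 | correlated | 4 | 6 | 4 | yes |

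In the uncorrelated case g22 = V22 − V11. That is admissible only if the week-24 variance is at least the baseline variance.

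**3. Size of the ambiguity (assumed inputs).** Take SD 10 at both visits and correlation 0.6, so (V11, V12, V22) = (100, 60, 100). Solving gives g11 = 100 − s, g12 = s − 40, g22 = 80 − 2s. The determinant g11·g22 − g12² equals (s − 40)(s − 160), so every s from 0 to 40 is valid.

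| s | 0 | 10 | 20 | 30 | 40 |
|---|---|---|---|---|---|
| SD of slopes, √(80 − 2s) | 8.9 | 7.7 | 6.3 | 4.5 | 0 |

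All five reproduce the same covariance exactly.

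**4. Effect on the treatment test, complete data.** One simulated two-visit data set with 40 per group had pooled covariance (0.9665, 0.5476, 1.2365). The variance of change is 0.9665 + 1.2365 − 2 × 0.5476 = 1.1078, so the SE of the interaction is √(1.1078 × 2/40) = 0.2353. Residual variances of 0.01, 0.10, 0.20, 0.30 and 0.35, each with its matching random-effects matrix, gave the same REML log-likelihood (−81.0575), interaction (0.8034) and SE (0.2353). The random-intercept model and the change-score t-test gave the same estimate and SE. Fitted with software, the intercept-plus-slope model converged. Different optimisers returned different splits (residual variance 0.403 or 0.379, slope variance 0.301 or 0.349) with the same interaction. In 20,000 simulated trials per setting, the change-score test had type I error 0.050 to 0.051, with or without true slope variation.

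**5. Effect of the fallback when week 24 is missing.** For a given covariance, the fitted week-24 mean in an arm is the completers' week-24 mean plus β × (baseline mean of all − baseline mean of completers), where β = V12/V11. Assume SD 10 at baseline, 15 at week 24 and correlation 0.6. Then V12 = 0.6 × 10 × 15 = 90 and the true β = 90/100 = 0.90. A random intercept forces equal variances. Pooling gives (100 + 225)/2 = 162.5, so β is about 90/162.5 = 0.55. Each unit by which completers' baseline mean differs from the whole arm's therefore moves that arm's estimate by about 0.90 − 0.55 = 0.35. With equal variances both values are 0.6 and the shift vanishes.

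Two sets of simulated trials used these SDs, baseline-dependent dropout in one arm and no true effect. Mean estimates were 0.72 (random intercept) against −0.18 (unstructured) in one set of 400, and 0.89 against 0.07 in the other. In the first set the gap was about one third of the SE. The two structures disagreed on significance in 3.5% and 4% of runs. With equal variances they nearly agreed (gap 0.11 in the first set).

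**The case against.** The strongest reply is that nothing the plan tests is touched. Hypothesis 1.1 rests on the fixed interaction, which depends only on the marginal 2x2 covariance, and that is identified. No hypothesis uses individual slopes. Baseline-carried-forward and completer analyses have both visits for every participant (given an observed baseline), so the natural alternatives agree there. This stands.

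The covariance of the random effects is also unstated, and uncorrelated effects would be just identified. That is correct, but it does not rescue the text. The plan does not choose that structure, and the structure fails if variance falls from baseline to week 24.

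One could also read the singular wording about a subject-specific effect, and the use of an intra-class correlation in section 5.2, as implying a random intercept only. The explicit sentence on slopes and intercepts contradicts that reading.

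A reader might infer that the Hypothesis 1.1 model cannot be validly fitted, or that software is bound to fail. The documents support neither. The fit in the working converged with an unchanged treatment estimate, and the three-visit Hypothesis 1.1 outcomes are identified.

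**Conclusion.** The concern holds as a specification flaw limited to PA outcomes measured only at baseline and week 24. With a residual and correlated random effects, the variance components and individual slopes are not identified: four parameters against three moments. This follows from the stated schedule and needs no assumed values.

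The complete-data treatment estimate, its SE, type I error, power and sample size are unaffected. The practical exposure is the unplanned choice of fallback in the all-available-data analysis. Its size is conditional. It is close to nil with equal variances, and about one third of an SE if the week-24 SD is 15 against 10 and dropout in one arm depends on baseline. Those SDs, the correlation and the dropout pattern are assumptions; the documents give none of them. The numerical agreement in step 4 comes from one simulated data set without extra covariates, but the algebra behind it is general for complete data.

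**What to change.** In section 5.1, limit the random-slope sentence to outcomes with three or more time points. For outcomes measured only at baseline and week 24, specify an unstructured 2x2 within-participant covariance, keep the group-by-visit interaction as the test, and drop the statement that individual slopes will be estimated. Name the unstructured form alone rather than offering a random intercept as an alternative, because the latter imposes equal variances and is where the MAR estimate can drift.

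The cost is about two sentences of analysis-plan wording, best settled before outcome data are examined. Visits, sample size, alpha and stated power do not change.

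### Free improvement: the Section 5.1 models estimate a separate baseline mean for each arm and plan no adjustment for the baseline outcome, which gives up precision at about 40 analysable participants per arm

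*Combined protocol and SAP*

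**What the plan says.** Section 5.1 uses one model form for every hypothesis. For the two-visit physical activity outcomes: "The models will regress PA measures on group (iSTEP vs. control), time (2 time points), and their interaction". For the cardiovascular risk factors: "The models will regress the outcomes on group (control, iSTEP PA/SB, iSTEP PA/SB + MedDiet), time (3 time points), and their interaction". The accelerometer outcomes and the cognition score (Hypotheses 1.2 and 2.2) are handled in the same way over three visits. The treatment test is the interaction: "A significant interaction term ($p<0.05$) would indicate a significant treatment effect".

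The only covariate rule is this: "Baseline characteristics found to be different between the groups will be used as covariates in the primary analyses". It follows a comparison of baseline characteristics for which age and gender are the examples. The baseline value of the outcome is not named.

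Three analysis sets are planned: "the inclusion of all available data, assuming values missing at random", a set with baseline carried forward (BOCF), and completers only. On random effects the plan says: "Subject-specific random effects will estimate individual changes in outcomes (slopes) as well as individual baseline values (intercept").

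Section 5.2 assumes 20% dropout, "leaving N=40 for each of the three groups", and for two-visit outcomes it powers "the difference in mean change in outcomes from baseline to week 24 visit". It claims at least 80% power for a medium to large effect with two visits and for a large effect with three.

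**The concern.** When baseline is a response and the group term is free, the model spends information on a baseline difference whose expected value is already known to be zero. With complete two-visit data the interaction is exactly the difference in mean change. A change score subtracts the whole baseline value, whatever the correlation, and this is usually not the most precise use of it. A random intercept does not alter this: it describes variation between participants and leaves the group contrast at baseline free.

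The covariate rule does not fill the gap. It operates only after a chance imbalance has been seen, and it does not prespecify the baseline outcome.

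The plan claims 80% power only for fairly large effects, so precision that costs no participants or visits is worth having.

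A secondary point concerns wording. The covariance between random intercept and random slope is not stated. If the two are correlated, the two-visit model has more variance parameters than the data can identify.

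**Working it through.** **Inputs from the documents.** 150 participants randomised, 50 per arm (protocol summary); 20% dropout, 40 per arm (Section 5.2); two-sided α = 0.05 (Section 5.1).

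**Assumed, because the readable text gives no value.** Within-subject correlation ρ from 0.3 to 0.8, and k = follow-up SD / baseline SD, set to 1 and then 1.2. Section 5.2 says that power depends on the correlation, but Figures 1a and 1b are not available to read.

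**Step 1: the plan's own figures.** 50 × (1 − 0.20) = 40 per arm, as stated. With 40 v 40 and 80% power, the noncentral t gives a detectable d of 0.634 change-score SDs. This lies between 0.5 and 0.8 and fits the two-visit description of medium to large. The plan's numerical d cannot be checked without the figures.

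**Step 2: variance of the treatment effect, in units of baseline variance.**

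- Completers: ratio adjusted/planned = k²(1 − ρ²) / (1 + k² − 2ρk). At k = 1 this is (1 + ρ)/2.
- All available data (50 baselines, 40 follow-ups), per arm: planned = k²(1 − ρ²)/40 + (1 − ρk)²/50; common baseline mean = k²(1 − ρ²)/40.
- BOCF, 20% carried forward, dropout unrelated to outcome, k = 1: effective ρ = 0.8ρ + 0.2; ratio = (1 + effective ρ)/2.

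Example for all available data at ρ = 0.5, k = 1: 0.75/40 = 0.01875 and 0.25/50 = 0.005, so the ratio is 0.01875/0.02375 = 0.79.

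**Step 3: results.** Each cell gives the variance ratio and, in brackets, the power when the planned test has 80%.

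| Analysis set | ρ = 0.3 | ρ = 0.5 | ρ = 0.7 | ρ = 0.8 |
|---|---|---|---|---|
| Completers, k = 1 | 0.65 (94%) | 0.75 (90%) | 0.85 (86%) | 0.90 (84%) |
| All available, k = 1 | 0.70 (92%) | 0.79 (88%) | 0.88 (85%) | 0.92 (83%) |
| BOCF, k = 1 | 0.72 (91%) | 0.80 (88%) | 0.88 (85%) | 0.92 (83%) |
| All available, k = 1.2 | 0.80 (88%) | 0.89 (84%) | 0.97 (81%) | 0.998 (80%) |

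For completers at k = 1.2 the ratio is 1.08/1.24 = 0.87 at ρ = 0.5 and 0.7344/0.76 = 0.97 at ρ = 0.7. The gain is zero when k = 1/ρ.

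In the all-available set at ρ = 0.5 and k = 1, the detectable difference falls from 0.62 to 0.55 baseline SDs. For completers the same case is worth 40/0.75 = 53.3 per arm instead of 40.

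**Step 4: three visits.** Under compound symmetry, k = 1 and 50/40/40 observed, the generalised least squares variance ratio for the week-24 or the week-48 contrast is again 0.70, 0.79, 0.88, 0.92. If time is linear and the test is on the slope, it is 0.65, 0.77, 0.87, 0.91.

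**Step 5: simulation.** With two visits and 40 completers per arm (k = 1), change-score against ANCOVA power was 80.5% v 93.2% at ρ = 0.3, 80.4% v 89.8% at 0.5, 80.0% v 85.5% at 0.7 and 80.8% v 84.3% at 0.8. Type I error was 4.6% to 5.6% across both methods.

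**Step 6: the random slope with two visits.** Two visits supply three covariance elements (two variances and one covariance). A residual, an intercept variance, a slope variance and their covariance make four parameters. With time coded 0 and 1, the sets (residual 1, intercept 2, slope 0.5, covariance 0.1) and (0.5, 2.5, 1.5, −0.4) both give 3.0 for the baseline variance, 2.1 for the covariance and 3.7 for the follow-up variance. The data cannot tell them apart. With independent random effects there are three parameters for three elements, and the model is just identified.

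**The case against.** The strongest reply is that nothing here is an error. The plan defines the effect as a difference in mean change and, for two-visit outcomes, powers that same quantity, so the analysis and the power statement agree. That stands, and it is why this is an optional improvement.

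The second reply is that equal SDs favour the point. If the random intercept and slope are independent, the follow-up variance is the baseline variance plus the slope variance, so k is at least 1. At k = 1.2 the all-available gain at ρ of 0.7 or more is about one percentage point of power or less. This also stands: the 92% and 94% figures are the favourable end of a range, not estimates for this trial. With the covariance known, however, the adjusted variance is never larger than the planned one.

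Third, the three-visit ratios in the table's form apply to single-visit contrasts, whereas Section 5.1 speaks of slopes and of an overall interaction. The slope ratios in Step 4 are slightly more favourable, so the conclusion does not depend on this. It is fair to say that a model with categorical visit must name the contrast that tests each hypothesis, and that the data-triggered covariate rule must not bring the baseline outcome in a second time. Both are matters of wording and are covered in the fix.

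Fourth, the random-slope point depends on a structure that the plan does not state, and it need not affect the interaction estimate or its standard error. That is correct. The point is secondary, and the main one does not rest on it.

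**Conclusion.** The point holds as a free gain in precision. The planned tests are valid, but they leave the baseline difference free and do not prespecify use of the baseline outcome. In the all-available analysis with equal SDs, the variance falls by 30% at ρ = 0.3, 21% at 0.5, 12% at 0.7 and 8% at 0.8, taking 80% power to between 92% and 83%. At k = 1.2 the range is 88% down to 80%.

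The size rests on assumed ρ and k, on 20% dropout and, for three visits, on compound symmetry. The gain is material for outcomes with low to moderate stability and negligible for very stable outcomes or those whose spread grows during follow-up. The arm definition does not matter: pooling both intervention arms against control (80 v 40) leaves the ratios unchanged.

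**What to change.** Amend Section 5.1 as follows.

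- For all hypotheses, use a repeated-measures model with categorical visit, unstructured within-subject covariance and one baseline mean common to all arms. Randomisation justifies the constraint. Participants with only a baseline value stay in, so the all-available-data analysis is preserved.
- For two-visit outcomes in the completer and BOCF sets, ANCOVA of week 24 on group and baseline is the simple equivalent.
- Name the contrast that tests each hypothesis: week 24, week 48 or a joint test.
- State that the baseline outcome is handled in this way and is outside the data-triggered covariate rule.
- Delete the random slope for two-visit outcomes.

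The cost is SAP wording and the matching analysis code. The baseline values are already collected, and no participants or visits are added. Unstructured covariance needs 3 parameters for two visits and 6 for three. The change should be made before outcome data are seen by arm, because a later choice between adjusted and change-score results would be open to challenge.
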